Amendment 01	02 August 2021	TMF-13865997
Original Protocol	16 April 2021	TMF-12458678

Amendment 04 (16 Dec 2024)

This amendment is considered to be substantial based on the criteria defined in Article 10(a) of Directive 2001/20/EC and EU Clinical Trial Regulation No. 536/2014 of the European Parliament of the European Parliament and the Council of the European Union.

Overall Rationale for the Amendment

This protocol has been amended to change the number of participants, clarified the end of study visits for participants who do not enter the expanded access program (EAP), the prohibited medications (anti-IL-5 and anti-IL-5-receptor therapies), and the T-cell profile sample.

List of main changes in the protocol and their rationale:

Section # and title	Description of Change	Brief Rationale
Sponsor signatory	Updated new sponsor signatory	Change in sponsor signatory
Section 1.1 Synopsis Section 3. OBJECTIVES AND ENDPOINTS Table 3 Objectives and Endpoints	Updated Objectives, Endpoints, and Estimands, by the removal of assessment of biological response to mepolizumab in participants aged 6 to 17	Removal of one of the endpoint regarding peripheral blood genomic and transcriptomic analysis

Section # and title	Description of Change	Brief Rationale
Section 1.3 Schedule of Activities	Added the missing concomitant medication check on follow up visit	Updated the Schedule of Activities Table
Section 1.3 Schedule of Activities Table 1, Footnotes Section 10.2 Clinical Laboratory Tests Table 8, Footnotes	Updated the footnote 14 in Table 1 Updated the footnote numbers 23, 24 and 25. as it was erroneously captured Updated the footnote 1 in Table 8	To provide clarification on Local lab eosinophil count results will be entered in eCRF Updated the footnotes to rectify the error
Table 3 Objectives and Endpoints Section 8.1.3 Reduction of Use of OCS, Immunosuppressive and/or Cytotoxic HES Therapy	Minor clarification regarding the outcome and population of interest when assessing reductions in immunosuppressive and/or cytotoxic HES therapy at Week 52	Clarified that the outcome of interest is those participants that are taking and not taking immunosuppressive and/or cytotoxic HES therapy at Week 52. Clarified that the population of interest is those participants that are taking immunosuppressive and/or cytotoxic HES therapy at baseline.
Section 4.1 Overall Design Section 5 Study Population Section 9.2 Sample Size Determination Section 10.1.4 Recruitment Strategy	Sample size reduced from 25 participants to 15 participants	Clarification of the change in sample size requirements, with at least 11 participants to be children (aged 6 to 11 years) and at least 4 participants to be adolescents (aged 12 to 17 years)
Section 4.4 End of Study (EOS) Definition	Clarification of the EOS for participants who enter or not enter expanded access program (EAP)	Updated the End of Study Definition
Section 6.8 Concomitant Therapy	Updated the concomitant medication with the prohibited medications	To provide additional information on permitted and prohibited concomitant medications
Section 8.3.4 Regulatory Reporting Requirements for SAEs	Update the section to provide an assessment of causality by the investigator	To comply with the new GSK protocol template requirements
Section 8.3.8 Medical Device Deficiencies	Provided information on regarding the usage of medical devices	To comply with the new GSK protocol template requirements

Section # and title	Description of Change	Brief Rationale
Section 8.7 T-cell profile	Updated the section for using the results of T-cell profile during Visit 2	To provide clarity on the use of results of T-cell profile
Section 9.4.3 Other Endpoints	
Re-instating text regarding the handling of the exploratory endpoint "Taking immunosuppressive and/or cytotoxic HES therapy at Week 52 in participants that are taking immunosuppressive and/or cytotoxic HES therapy at baseline"
 
Clarification added regarding the annualised flare rate during the study to be compared with the annualised flare rate in the year prior to Screening (Visit 1) for each patient.
	
Clarified wording that premature study withdrawal will be considered as a treatment failure within the assessment of this dichotomous exploratory endpoint.
 
Additional wording inserted to further clarify on the reporting of this exploratory endpoint on changes in HES flare rate.

Section 10.1.3 Informed Consent and Assent Process	Addition of a paragraph on the time of storage of collected samples	To comply with the new GSK protocol template requirements
Section 10.1.5.Data Protection	Statement regarding protection of the personal data and GSK internal policy was added	To comply with the new GSK protocol template requirements

1. PROTOCOL SUMMARY

1.1. Synopsis

Protocol Title: A Phase 3, 52-week, open-label, single arm study to investigate the efficacy and safety of mepolizumab SC in participants aged 6 to 17 years with hypereosinophilic syndrome.

Brief Title: Study in Paediatrics with HypEREosinophilic syndrome (SPHERE)

Rationale:

Hypereosinophilic syndrome (HES) is a group of rare haematological disorders without a known cause in which eosinophils are overproduced in the bone marrow for prolonged periods of time. The goal of HES treatment is to relieve symptoms and to reverse or delay progression of any further organ damage caused by activated eosinophils. Mepolizumab has been shown to be efficacious and well tolerated in patients with HES.

[figure not shown]
The purpose of this study is to investigate the efficacy and safety of mepolizumab SC in children (aged 6 to 11 years) and adolescents (aged 12 to 17 years) with HES who are receiving standard of care (SoC) therapy. The primary objective of the study is to evaluate the efficacy of mepolizumab SC given every 4 weeks in participants aged 6 to 17 years with HES.

Objectives, Endpoints, and Estimands:

Objectives	Endpoints
Primary	

 To evaluate the efficacy of mepolizumab SC given every 4 weeks in participants aged 6 to 17 years with HES 	
 Frequency of HES flares over the 52-week study treatment period
Secondary	

 To assess the effect of mepolizumab SC given every 4 weeks on the change in oral corticosteroid (OCS) dose in participants aged 6 to 17 years with HES that are taking OCS at baseline 	
 Change in the mean daily OCS dose (prednisone/prednisolone or equivalent) from Weeks 0 to 4 to Weeks 48 to 52 Reduction of $\geq 50\%$ in mean daily OCS dose (prednisone/prednisolone or equivalent) from Weeks 0 to 4 compared with Weeks 48 to 52 Achieving a mean daily OCS dose (prednisone/prednisolone or equivalent) of ≤ 7.5 mg during Weeks 48 to 52

 To assess the effect of mepolizumab SC given every 4 weeks on the change in oral corticosteroid (OCS) dose in participants aged 6 to 17 years with HES 	
 Achieving a mean daily OCS dose (prednisone/prednisolone or equivalent) of ≤ 7.5 mg during Weeks 48 to 52

Objectives	Endpoints

 To assess the efficacy of mepolizumab SC given every 4 weeks on fatigue in participants aged 12 to 17 years with HES 	
 Change from baseline in fatigue severity based on weekly average score of Brief Fatigue Inventory (BFI) item 3 (worst level of fatigue during past 24 hours) for Week 52

 To evaluate the immunogenicity of mepolizumab SC given every 4 weeks in participants aged 6 to 17 years with HES 	
 Occurrence of anti-drug antibodies (ADA) and neutralising antibodies (NAb)

 To assess the effect of long-term use of mepolizumab SC on a pharmacodynamics (PD) marker in participants aged 6 to 17 years with HES. 	
 Ratio to baseline in absolute blood eosinophil count at discrete time points during the 52-week study treatment period

 To assess the pharmacokinetics (PK) of mepolizumab SC in participants aged 6 to 17 years with HES 	
 Mepolizumab plasma concentration at discrete time points during the 52-week study treatment period
Other	

CCI

Objectives	Endpoints
CCI	

 To evaluate the safety of mepolizumab SC given every 4 weeks in participants aged 6 to 17 years with HES 	
 Occurrence of adverse events (AEs) and serious adverse events (SAEs) Change from baseline in vital signs (blood pressure, heart rate and temperature) Change from baseline in 12-lead electrocardiogram (ECG) Haematological and clinical laboratory tests

Primary estimand

The primary clinical question of interest is: What is the rate of HES flares during 52 weeks of mepolizumab SC given every 4 weeks in participants aged 6 to 17 years, regardless of treatment discontinuation for any reason and regardless of changes in background therapy?

The estimand is described by the following attributes:

- Population: participants with HES aged 6 to 17 years with or without maintenance SoC therapy
- Treatment condition: Mepolizumab given every 4 weeks in addition to SoC
- Variable/endpoint: frequency of HES flares over 52 weeks
- Summary measure: annualised rate of HES flares

- Intercurrent events:
 - Study treatment discontinuation – treatment policy strategy
 - Change in background HES medication (other than changes due to a clinically documented flare) - treatment policy strategy
- Rationale for estimand:
 - Interest lies in the rate of flares when medication is taken for the entire study duration. For participants discontinuing study medication or changing background medication, use of a treatment policy strategy recognises that this could be due to an unfavourable cause.

Secondary efficacy estimands

Secondary efficacy estimands address changes in OCS use and effects on fatigue severity.

Estimands for changes in OCS use will use the subpopulation of participants with HES aged 6 to 17 years who are taking OCS at baseline. Treatment condition will be the same as for the primary estimand. The following 3 endpoints and summary measures will be used:

1. Endpoint: Change in the mean daily OCS dose (prednisone/prednisolone or equivalent) from Weeks 0 to 4 to Weeks 48 to 52; summary measure: mean across participants.
2. Endpoint: Reduction of $\geq 50\%$ in mean daily OCS dose (prednisone/prednisolone or equivalent) from Weeks 0 to 4 compared with Weeks 48 to 52; summary measure: proportion of participants with this reduction.
3. Endpoint: Achieving a mean daily OCS dose (prednisone/prednisolone or equivalent) of ≤ 7.5 mg during Weeks 48 to 52; summary measure: proportion of participants with this level of OCS usage.

For the intercurrent event of study treatment discontinuation, a treatment policy strategy will be used. Use of OCS is part of the endpoint (composite strategy). Other changes in background HES medication will use a treatment policy strategy.

An additional estimand for changes in OCS use will use the whole population of participants with HES aged 6 to 17 years. Treatment condition will be the same as for the primary estimand. The following endpoint and summary measure will be used:

- Endpoint: Achieving a mean daily OCS dose (prednisone/prednisolone or equivalent) of ≤ 7.5 mg during Weeks 48 to 52; summary measure: proportion of participants with this level of OCS usage.

For the intercurrent event of study treatment discontinuation, a treatment policy strategy will be used. Use of OCS is part of the endpoint (composite strategy). Other changes in background HES medication will use a treatment policy strategy.

The secondary estimand for fatigue severity will use the subpopulation of participants with HES aged 12 to 17 years. Treatment condition will be the same as for the primary estimand. A treatment policy strategy will be used for the intercurrent events of study treatment discontinuation and changes to background HES therapy. The endpoint will be the change from baseline in weekly average score of the BFI item 3 (worst level of fatigue during past 24 hours) for Week 52 and the summary measure will be the mean value.

Overall Design:

This is a 52-week, open-label, single arm, multicentre study of SC mepolizumab in children and adolescent participants with HES receiving SoC therapy.

Brief Summary:

The purpose of this study is to investigate the efficacy and safety of SC mepolizumab in paediatric participants aged 6 to 17 years with HES.

Approximately 15 participants who are on a stable dose of HES therapy for at least 4 weeks prior to Visit 2 will be enrolled. All eligible participants will receive mepolizumab, with the first dose administered at Visit 2, and subsequent doses administered every 4 weeks over a treatment period of 52 weeks (with a last dose at 48 weeks).

Concomitant SoC therapy may be adjusted as needed from 4 weeks after the first dose of mepolizumab. All participants will be managed during the study according to routine medical care.

All participants will attend a study-site visit at Screening (Visit 1), Baseline (Visit 2), Week 4 (Visit 3), Week 8 (Visit 4), Week 24 (Visit 8), and the Week 52 exit visit (Visit 15). The other study visits may be performed remotely where applicable country and local regulations allow. Home healthcare services may also be utilised to support these activities where local regulations and infrastructure allow. The final visit of the treatment period will be at Week 52. There is a follow-up visit at Week 60, 8 weeks after the Week 52 visit (12 weeks after the last dose of mepolizumab).

Eligible participants may enter an expanded access program (EAP), where available, immediately after completion of the 52-week study period. Participants who withdraw from the study prematurely will not be considered for an EAP.

Number of Participants:

The number of participants was selected based on practical considerations. At least 15 participants aged 6 to 17 years will be enrolled and receive at least 1 dose of mepolizumab. Due to the rare nature of HES in paediatrics, there is minimal data available to predict the age distribution in the study. CCI

Note: "Enrolled" means a participant, or their legally acceptable representative, agrees to participate in a clinical study following completion of the informed consent process. Potential participants who are screened for the purpose of determining eligibility for the study, but do not participate in the study, are not considered enrolled, unless otherwise specified by the protocol.

[figure not shown]
Intervention Groups and Duration:

All participants will receive active treatment with mepolizumab SC injection every 4 weeks over a treatment period of 52 weeks (with last dose at 48 weeks). CCI

Data Monitoring/ Other Committee: An Independent Data Monitoring Committee (IDMC) will be utilised in this study.

1.2. Schema

Figure 1 Schema of Study Design

^aParticipants who enrol in an expanded access program (EAP) of mepolizumab are not required to have a follow-up visit.

1.3. Schedule of Activities (SoA)

The Schedule of Activities (SoA) is presented in [Table 1](#).

CONFIDENTIAL

215360
Protocol Amendment 4 Final

Table 1 Schedule of Activities

Procedures	Screen	Treatment Period and Exit Visit ¹															Early discontinuation /Withdrawal Visit		Follow-up
Study visit	1	2	3	4	5	6	7	8	9	10	11	12	13	14	15 Exit visit	Flare ²	Discontinue from study treatment Visit (replacing visits 2-15) ³	Withdrawal Visit	16
Study week	-2 to -4	0	4 (±7 days)	8 (±7 days)	12 (±7 days)	16 (±7 days)	20 (±7 days)	24 (±7 days)	28 (±7 days)	32 (±7 days)	36 (±7 days)	40 (±7 days)	44 (±7 days)	48 (±7 days)	52 (±7 days)				~12 wks After last dose (±7 days)
Informed consent ⁴	X																		
Eligibility assessments																			
Inclusion/Exclusion criteria	X	X																	
Demography/childbearing status assessment	X																		
Medical and treatment history	X																		
Parasite screening ⁵	X																		
Physical examination including height and weight	X							X							X				
Efficacy assessments																			
CCI																			
Concomitant medications including OCS		X	X	X	X	X	X	X	X	X	X	X	X	X	X	X	X	X	X
CCI																			
BFI item 3 ⁶																			
CCI																			

CONFIDENTIAL

215360
Protocol Amendment 4 Final

Procedures	Screen	Treatment Period and Exit Visit ¹															Early discontinuation /Withdrawal Visit		Follow-up
Study visit	1	2	3	4	5	6	7	8	9	10	11	12	13	14	15 Exit visit	Flare ²	Discontinue from study treatment Visit (replacing visits 2-15) ³	Withdrawal Visit	16
Study week	-2 to -4	0	4 (±7 days)	8 (±7 days)	12 (±7 days)	16 (±7 days)	20 (±7 days)	24 (±7 days)	28 (±7 days)	32 (±7 days)	36 (±7 days)	40 (±7 days)	44 (±7 days)	48 (±7 days)	52 (±7 days)				~12 wks After last dose (±7 days)

CCI

Safety assessments

AE/SAE assessment	X ¹¹	X	X	X	X	X	X	X	X	X	X	X	X	X	X	X	X	X	X
Vital signs ¹²	X	X						X							X	X		X	
ECG	X														X	X			

Laboratory assessments¹³

Haematology with differential	X ¹⁴	X	X	X	X	X	X	X	X	X	X	X	X	X	X	X	X	X	
Clinical and liver chemistry	X	X			X			X			X			X		X	X ¹⁵	X	
Pregnancy test ¹⁶	X	X	X	X	X	X	X	X	X	X	X	X	X	X	X		X ¹⁷	X	X
Urinalysis ¹⁸	X														X		X ¹⁵	X	
Hepatitis serology ¹⁹	X																		
Total IgE		X																	
F/P status ²⁰	X																		
T-cell profile	X																		
Immunogenicity		X						X							X		X ²¹	X	X
PK sample			X					X							X		X ²²	X	
IL-5		X																	

Investigational product

Study treatment administration ²³		X	X	X	X	X	X	X	X	X	X	X	X	X					
--	--	---	---	---	---	---	---	---	---	---	---	---	---	---	--	--	--	--	--

CONFIDENTIAL

215360
Protocol Amendment 4 Final

Procedures	Screen	Treatment Period and Exit Visit ¹															Early discontinuation /Withdrawal Visit		Follow-up
Study visit	1	2	3	4	5	6	7	8	9	10	11	12	13	14	15 Exit visit	Flare ²	Discontinue from study treatment Visit (replacing visits 2-15) ³	Withdrawal Visit	16
Study week	-2 to -4	0	4 (±7 days)	8 (±7 days)	12 (±7 days)	16 (±7 days)	20 (±7 days)	24 (±7 days)	28 (±7 days)	32 (±7 days)	36 (±7 days)	40 (±7 days)	44 (±7 days)	48 (±7 days)	52 (±7 days)				~12 wks After last dose (±7 days)
eCRF and eDiary																			
Register visit in IVRS	X	X	X	X	X	X	X	X	X	X	X	X	X	X	X		X	X	
Complete eCRF	X	X	X	X	X	X	X	X	X	X	X	X	X	X	X		X	X	X
eDiary registration and training	X																		
Dispense (D)/collect (C) eDiary	D ²⁴														C			C	
Review of eDiary ²⁵		X	X	X	X	X	X	X	X	X	X	X	X	X	X		X	X	

Abbreviations: AE, adverse event; BFI, Brief Fatigue Inventory; ECG, electrocardiogram; eCRF, electronic case report form; F/P, FIP1L1-PDGFRα fusion tyrosine kinase gene translocation; HCRU, healthcare resource utilisation; HES, hypereosinophilic syndrome; IgE, Immunoglobulin E; IL-5, Interleukin-5; IVRS Interactive Voice Response Systems; OCS, oral corticosteroid(s); **CCI**; RNA, ribonucleic acid; SAE, serious adverse event; **CCI**.

- Activities that will be performed only in clinic are greyed out. All participants will need to attend a clinic visit at Screening (Visit 1), Baseline (Visit 2), Week 4 (Visit 3), Week 8 (Visit 4), Week 24 (Visit 8), and the Week 52 exit visit (Visit 15). A Flare Visit follows routine medical practice. The other visits may be performed remotely where applicable country and local regulations and infrastructure allow. Eligibility criteria assessment data will all be captured on site. Data from efficacy assessments other than echocardiogram, ECG, and spirometry will be captured digitally via electronic devices and teleconferences or on site. Echocardiogram, ECG, and spirometry data will only be captured at site visits. Laboratory assessments other than haematology with differential, clinical and liver chemistry, pregnancy test, and PK samples are captured on site.
- Assessments will be collected when possible depending on the clinical status during worsening of symptoms between scheduled clinic visits to evaluate for a HES flare. When attending the clinic visit at the time of a suspected HES flare is not possible, the investigator should make every effort to evaluate the participant via telephone and complete the HES Core assessments v2.
- Subjects who prematurely discontinue study treatment will continue to attend 4-weekly scheduled Discontinuation Visits completing assessments as indicated. Participants who discontinue study treatment are not required to perform a Follow-up visit, unless they have not completed 12 weeks after last dose immunogenicity assessment within the 52 week study period.
- Informed consent must be obtained prior to starting Visit 1 procedures.
- Parasitic screening is only required in countries with high-risk or for participants who have visited high-risk countries in the past 6 months. Sites should use local laboratories.

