9. CCI [REDACTED]
[REDACTED]
10. When a CV flare is suspected during the study period based on investigator's judgement.
11. Only SAEs that are considered related to study procedures are to be collected from the time of signing informed consent.
12. Vital sign measurements will include temperature, systolic and diastolic blood pressure, and heart rate.
13. During the treatment period, all laboratory samples should be obtained pre-dose.
14. Eosinophil count samples for the screening visit only may be analysed by local labs if required. If a local sample is required, it is important that a sample for central analysis is obtained at the same time. Local lab eosinophil count results performed at the screening visit will be entered to the eCRF. If local lab samples are taken, a second sample will also be sent for central testing. The higher of the eosinophil cell count values is to be used to fulfil the entry criteria for enrolment.
15. Do not perform for each discontinuation visit, follow test frequency of Treatment Period schedule visit 2-15.
16. Negative urine pregnancy test result must be confirmed prior to dosing in female participants of reproductive potential. If a urine test cannot be confirmed as negative (e.g., an ambiguous result), a serum pregnancy test is required. In such cases, the participant must be excluded from participation if the serum pregnancy result is positive.
17. Pregnancy testing is only required until the end of systemic exposure, 12 weeks after the last dose.
18. Urine tests are done locally using dipstick. If found abnormal, the urine sample will be sent to the central laboratory for further testing.
19. If test was performed within 3 months prior to Visit 2, testing at Screening is not required. Test required are hepatitis B surface antigen and hepatitis C antibody. Participants with positive hepatitis C antibody due to prior resolved disease can be enrolled only if a confirmatory negative hepatitis C RNA test is obtained.
20. If no documented results are available.
21. For participants who discontinue treatment immunogenicity is to be performed 4 and 12 weeks after the last dose only.
22. For participants who discontinue treatment PK is to be performed 4 weeks after last dose only.
23. The date and time of the administration of study treatment will be recorded in the eCRF.

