6.2.4. Assessment Window

For summaries by visit, data recorded at an unscheduled visit will be re-assigned in the ADaM data sets to the closest nominal visit at which collection of data was scheduled, unless information already exists at that visit. Unscheduled data re-assigned to a scheduled visit will be included in analyses, summary tables and figures by scheduled visit. Unscheduled data that is not re-assigned to a scheduled visit will not be included in analyses, summary tables or figures by scheduled visit. Unscheduled data that is not re-assigned to a scheduled visit will be considered in the derivation of baseline and highest/worst case post baseline result for relevant summary tables.

Data recorded at the early withdrawal visit will be re-assigned in the ADaM data sets to the next scheduled visit, unless information already exists at that visit. Early withdrawal data re-assigned to a scheduled visit will be included in analyses, summary tables and figures by scheduled visit. Early withdrawal visit data that is not re-assigned to a scheduled visit will not be included in analyses, summary tables or figures by scheduled visit, but will be considered in the derivation of highest/worst case post baseline result for relevant summary tables.

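### Table 1 schedules no ECG, vital signs or height/weight after a child stops drug, in conflict with the text that keeps all participants to the Week 24 and Week 52 visits

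*Protocol*

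**What the plan says.** **Schedule after drug stop.** Footnote 3 of Protocol Table 1 reads: "Subjects who prematurely discontinue study treatment will continue to attend 4-weekly scheduled Discontinuation Visits completing assessments as indicated". The matching column is headed "Discontinue from study treatment Visit (replacing visits 2-15".

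**The three assessments.**
- The row "Physical examination including height and weight" is marked at Visits 1, 8 and 15 only.
- Vital signs (footnote 12: "Vital sign measurements will include temperature, systolic and diastolic blood pressure, and heart rate") are marked at Visits 1, 2, 8 and 15, Flare and Withdrawal.
- ECG is marked at Visits 1 and 15 and Flare.

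**How other tests are carried over.** Clinical chemistry and urinalysis are marked in the Discontinuation column under footnote 15: "Do not perform for each discontinuation visit, follow test frequency of Treatment Period schedule visit 2-15". Pregnancy testing, immunogenicity and PK have their own discontinuation footnotes (17, 21 and 22).

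**Text that points the other way.** Footnote 1 and Section 4.1 require every participant to come to site at Week 24 (Visit 8) and Week 52 (Visit 15), with no exception for those off drug. Section 7.1 keeps participants who stop drug in the study, where possible, until Visit 15. Section 4.4 counts a participant as completing at the Week 52 visit whether or not treatment was received throughout.

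**What depends on the data.** Protocol Sections 1.1 and 3 list "Change from baseline in vital signs (blood pressure, heart rate and temperature") as an endpoint, and also change from baseline in 12-lead ECG. SAP 4.7.3.2 summarises height, weight and vital signs by visit, and SAP 4.7.3.3 does so for ECG change. SAP 6.2.4 sends unscheduled data to be "re-assigned in the ADaM data sets to the closest nominal visit at which collection of data was scheduled", unless that visit already has a value.

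**The concern.** Stopping drug is meant to change treatment, not follow-up. If sites work from the Discontinuation column, follow-up of these safety measures stops as well. The by-visit summaries on the full analysis set would then describe mainly children who completed treatment. Those who stopped, possibly because of harm, would be missing without the summary showing it. With about 15 participants, one or two such absences are visible in every Week 52 summary.

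The SAP can also hide the gap. If the Week 52 ECG cell is empty, its rule for unscheduled data can fill the cell with an ECG taken at a flare months earlier. The table would then look complete while containing a value from another time and another clinical state.

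**Working it through.** No figure in the plan needs reproducing. The check is a reading of Table 1, a count of scheduled measurements, and two short calculations.

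**1. Table 1 marks.** Each row splits into 19 columns (Visits 1 to 15, Flare, Discontinuation, Withdrawal, Visit 16). None of the three rows at issue carries a redacted footnote.

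| Row | Visits 1–15 | Flare | Discontinuation | Withdrawal |
|---|---|---|---|---|
| ECG | 1, 15 | X | blank | blank |
| Vital signs | 1, 2, 8, 15 | X | blank | X |
| Height/weight | 1, 8, 15 | blank | blank | blank |
| Urinalysis | 1, 15 | blank | X (fn 15) | X |
| Chemistry | 1, 2, 5, 8, 11, 14 | X | X (fn 15) | X |

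Urinalysis is the useful comparison. It has the same treatment-period pattern as ECG, yet it is carried into the Discontinuation column. If Visit 15 procedures applied automatically after drug stop, that mark would not be needed.

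**2. Count under the literal reading.** Dose k is given at Visit k + 1 (dose 1 at Visit 2, dose 7 at Visit 8, dose 13 at Visit 14). For a child whose last dose is dose k, with k from 1 to 12, Visits k + 2 to 15 become Discontinuation visits. Scheduled measurements after Visit 2 are the marked visits v with 2 < v < k + 2.

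| Assessment | Last dose 1–6 | Last dose 7–12 | If Visits 8 and 15 are kept |
|---|---|---|---|
| ECG | 0 | 0 | 1 |
| Vital signs | 0 | 1 (Week 24, before the stop) | 2 |
| Height/weight | 0 | 1 (Week 24, before the stop) | 2 |

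After the stop itself, the scheduled count is 0 for all three. The exceptions are vital signs at a Withdrawal visit and unscheduled ECG and vital signs at a Flare visit.

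**3. Size.** With N = 15, one discontinuer is 1/15 = 6.7% of the Week 52 data, and d discontinuers are d/15. The documents give no expected d.

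**4. Re-assignment distance in SAP 6.2.4.** This takes the rule to mean the visit at which the particular test was scheduled. ECG has two nominal visits: Visit 1, at Week −4 to −2, and Visit 15, at Week 52.
- Midpoint: (−4 + 52)/2 = 24 to (−2 + 52)/2 = 25.
- A flare ECG after about Week 25 is therefore closer to Week 52 than to Visit 1, and can be up to about 52 − 25 = 27 weeks early.
- Before the midpoint, the nearest visit is Visit 1, which already holds a value, so nothing moves.
- For vital signs, the midpoint between Weeks 24 and 52 is (24 + 52)/2 = 38, so the largest shift into Week 52 is 52 − 38 = 14 weeks.

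**The case against.** The strongest reply is that the text overrides the column heading. Footnote 1 and Section 4.1 bring everyone to site at Weeks 24 and 52, and Visit 15 carries all three assessments. The eDiary is collected only at Visit 15 and Withdrawal, although Section 7.1 has discontinuers continue daily entries. If the Discontinuation column fully replaced Visit 15, a discontinuer who completed would never hand the eDiary in. The SAP's off-treatment phase also runs to the Week 52 visit. This reading is credible. The heading and the footnote 15 mark on urinalysis point the other way, so what stands is a conflict that sites may resolve differently.

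A reader might infer that these measures are never taken in children who stop drug. The documents do not support that. Flare visits include ECG and vital signs, Withdrawal includes vital signs, and a child who stops after the Week 24 visit already has Week 24 vital signs and height/weight. Section 8.2 also allows safety time points to be added, although only in response to newly available data.

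A reader might also infer that a child stopped under the QTc criteria has no post-baseline ECG. That is wrong too. Sections 7.1.2 and 8.2.3 base such a stop on the average of triplicate readings, so post-baseline ECGs exist. Nor are children who stop for harm left unfollowed: Section 8.3.3 follows SAEs and events of special interest to resolution, and adverse events and haematology stay marked at Discontinuation visits.

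Three limits on importance also stand. The ECG and vital-sign endpoints sit under Other objectives, and height/weight is an SAP summary rather than a stated endpoint. A Week 52 ECG in a child last dosed at Week 16 comes 36 weeks after that dose, so it completes the by-visit summary but says little about effects near the stop. The re-assignment problem arises only when the Week 52 cell is empty, and ECG reporting follows sponsor standards that are not in these documents.

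**Conclusion.** The point holds as an internal conflict with a definite consequence under one of its two readings. The Discontinuation column schedules none of the three assessments, and the Withdrawal column lacks ECG and height/weight. The text on attendance at Weeks 24 and 52 and follow-up to Visit 15 suggests otherwise.

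If sites follow the column, a child who stops after any of doses 1 to 12 and stays in the study has no scheduled post-baseline ECG, and no scheduled vital signs or height/weight after the stop. The Week 52 summaries then rest mainly on treatment completers, with about 7% of the planned sample lost per discontinuer. If sites follow the text, the loss does not occur.

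The size rests on N = 15 and the literal reading; the total cannot be stated because the plan does not forecast discontinuations. The SAP relabelling of up to about 27 weeks for ECG rests on a test-by-test reading of SAP 6.2.4 and on an empty Week 52 cell. The matter should be corrected, but it does not affect the primary endpoint.

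**What to change.** **Protocol Table 1.** Reconcile the column heading with footnote 1 and Sections 4.1, 4.4 and 7.1. Mark ECG, vital signs and physical examination with height/weight in the Discontinuation column under a footnote like footnote 15, so that they follow the Visit 2 to 15 frequency. Mark ECG and height/weight in the Withdrawal column.

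**SAP 6.2.4.** Add one sentence that sets a maximum distance for moving unscheduled data to a nominal visit, and keep values outside it for listings and worst-case summaries only.

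**Cost.** A footnote, a few table marks and one SAP sentence. No discontinuer would have more of these procedures than a treatment completer. The downside is site attendance at Weeks 24 and 52, since footnote 1 states: "Echocardiogram, ECG, and spirometry data will only be captured at site visits". The same footnote already asks that attendance of every participant. The change completes the by-visit summaries; it does not add a measurement close to the time of stopping for children who stay in the study.
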